3.1 Type/Design of the Trial

Oral Standard-of-Care Antipsychotic Treatment(s) (Retrospective Phase)

To be eligible for trial participation, subjects must have been prescribed oral antipsychotic standard-of-care pharmacotherapy for at least 6 months or longer, with evidence of prescription (i.e., pharmacy records) during the retrospective phase and prior

Protocol 31-201-301 Interim Analysis Plan

to screening. Subjects administered antipsychotics other than aripiprazole must cross-titrate onto oral aripiprazole during the screening period at the discretion of the investigator to be eligible for trial participation.

Screening

After providing informed consent, subjects will enter the 45-day (Days -45 to -1; approximately 6 weeks) screening period to determine if they are eligible to enter the Abilify MyCite treatment (prospective) phase. The subject's past psychiatric history for the 6 months prior to screening must be available, inclusive of a comprehensive review of all psychiatric hospitalizations and interventions (psychiatric only).

As safety of the subject dictates, 2 options are available to the investigator as subjects transition from the screening period to the Abilify MyCite treatment (prospective) phase:

- 1) Antipsychotic medications other than oral aripiprazole may be tapered off and/or discontinued during the screening period prior to the subject receiving the first treatment with Abilify MyCite.
- 2) Antipsychotic medications other than oral aripiprazole may be continued during the screening period and cross-titration with oral aripiprazole trial drug may occur. Some investigators may choose this option for the subject depending as local practice patterns dictate and on the subject's safety.

Abilify MyCite treatment (prospective) phase

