For subjects enrolled in the trial, those not on aripiprazole at screening and who need to cross-titrate will do so during the screening period for conversion to aripiprazole from other antipsychotics according to the approved labels. At the baseline visit (Day 1), Abilify MyCite onboarding will be provided with informational materials and additional call center support. Initiation of Abilify MyCite treatment will commence at the baseline (Day 1) visit, with subjects ingesting the Abilify MyCite tablet embedded with an IEM sensor product, wearing the patch, and using the smartphone app for up to 6 months, including a required 3 months (Months 1 to 3) of Abilify MyCite treatment. This will be followed, at investigator discretion, to either change to oral standard-of-care antipsychotic treatment (eg, oral or LAI) or remain on Abilify MyCite for the second 3-month period (Months 4 to 6), during the prospective phase. The first dose of Abilify MyCite is to be taken at the baseline (Day 1) visit (in the clinic) during onboarding, unless they have already taken their daily dose. Subjects should not take their oral standard-of-care medication that morning before the baseline (Day 1) visit.

During the assessment period, subjects will visit the investigator for clinical evaluations at baseline (Day 1), Month 3, and Month 6/early termination (ET). Monthly assessments

Protocol 31-201-301 Interim Analysis Plan

will follow a 28-day schedule, and at each visit and at any unscheduled visits, the subject's clinical status will be evaluated. All hospitalizations and all interventions (psychiatric only as well as pharmacy cost of all medications) will be recorded, in addition to all other assessments outlined in this protocol. The primary endpoint will be assessed at Month 3. The final trial visit will be on Month 6/ET and will be followed by a 30-day (- 3/ + 2 day) safety follow-up period for subjects continuing on Abilify MyCite. For subjects completing Months 4 to 6 on standard of care, a 30-day safety follow-up period is not required. Subjects will also visit the clinic for medication dispensing and accountability at the scheduled visits. Any treatment changes, including reason for the change, will be recorded in the electronic case report form (eCRF).

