3.3 Study Population

The study population will include male and female subjects, 18 to 65 years of age, inclusive, with a diagnosis of schizophrenia according to DSM-5 criteria. Subjects must have had at least 1 inpatient psychiatric hospitalization within the 4 years (48 months) prior to screening but must not have been hospitalized for any psychiatric reason during the 4 weeks prior to signing the ICF or at any time during the screening period. Subjects must have been on oral antipsychotics treatment in the last 7 months prior to screening.

4 Sample Size and Power Justification

The primary endpoint of this trial compares the paired proportions of inpatient psychiatric hospitalization during the retrospective period (Month 1 to 3) and the prospective period (Month 1 to 3), which will be analyzed using a McNemar test.

Based on published results of other similar studies for the particular time periods

Protocol 31-201-301 Interim Analysis Plan

(retrospective Month 1 to 3 and prospective Month 1 to 3) we are evaluating, it is reasonable to assume that 15.5% of the subjects are hospitalized during retrospective Month 1 to 3 and 7% are hospitalized during prospective Month 1 to 3; about 5% of subjects who are not hospitalized retrospective will be hospitalized prospectively, while 13.5% of the subjects who are hospitalized retrospectively will not be hospitalized. With this assumption, 200 completed subjects will provide 80% power ($\alpha = 0.05$ two-sided) to detect a difference of 8.5% in the paired hospitalization proportions between pre-switch and post-switch periods while the proportion of total discordant pairs is 18.5%. In addition, this sample size will provide 80% power for the comparison of retrospective Month 4 to 6 vs prospective Month 4 to 6, assuming 30% of the subjects are hospitalized pre-switch (12.5% subjects will be hospitalized post-switch and another 17.5% won't have hospitalization post-switch) and, overall, 20% are hospitalized post-switch (among them, 12.5% subjects are hospitalized both pre-switch and post-switch and 7.5% have no hospitalization pre-switch).

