7.1.2 Technical Details

Inpatient psychiatric hospitalization is defined as closed (locked) ward or open ward inpatient psychiatric hospitalization, where the hospitalization is not primarily for psychosocial reasons.

The start date and end date of the retrospective period Months 1-3 are calculated in the following ways: start date = (Date signing informed consent - 28*6 Days) and end date = (Date of signing informed consent - 28*3-1 Days). The start date and end date of the prospective period Months are calculated as: start date = (Mycite start date) and end date = (Mycite start date + 28*3 - 1). Similarly, the start date and end date of the retrospective period Months 4-6 are calculated in the following ways: start date = (Date signing informed consent - 28*3 Days) and end date = (Date of signing informed consent -1 Days). The start date and end date of the prospective period Months are calculated as: start date = (Mycite start date + 28*3) and end date = (Mycite start date + 28*6 - 1).

Inpatient psychiatric hospitalization is deemed to occur during the retrospective (or prospective) Months 1-3 if:

- The hospitalization starts before the start date of retrospective (or prospective) Months 1-3 and continues into Months 1-3
- The hospitalization starts during the retrospective (or prospective) period.

Similarly, Inpatient psychiatric hospitalization is deemed to occur during the retrospective (or prospective) Months 4-6 if:

- The hospitalization starts before the start date of retrospective (or prospective) Months 4-6 and continues into Months 4-6
- The hospitalization starts during the retrospective (or prospective) period

All the above hospitalization in Months 1-3 and Months 4-6 will be counted in the Month 1-6 period.

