7.1.3 Sensitivity Analyses

As sensitivity analysis, the primary efficacy analysis will be performed on the mITT subjects who have completed the 3-month treatment only that is all subjects who are in study for at least 75 days (12 weeks adjusting for the 9 days allowed for visit window).

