Appendix 2 Table of Contents for Proposed Tables and Listings**Summary Tables:**

- CT-1.1 Subject Disposition by Site (Enrolled Sample)
- CT-2.1 Reasons for Discontinuation (ITT Sample)
- CT-2.2 Discontinuation from treatment / study due to COVID
- CT-3.1.1 Demographic Characteristics by Gender and Site and Overall (ITT Sample)
- CT-3.1.2 Demographic Characteristics by Gender and Site and Overall (Month 1-3 mITT)
- CT-3.2.1.1 Baseline Disease Characteristics by Gender and Site and Overall (ITT Sample)
- CT-3.2.2.1 Baseline Disease Characteristics by Gender and Site and Overall (Month 1-3 mITT)
- CT-4.1.1 Medications Taken Prior to Start of Trial (Safety Sample)
- CT-4.2 Medications Taken During Trial (Safety Sample)
- CT-4.3 Medications Taken Post Trial (Safety Sample)
- CT-4.4.1 Listing of ConMeds due to COVID
- CT-4.4.2 Summary of Protocol Deviations (ITT Sample)

Protocol 31-201-301 Statistical Analysis Plan

CT-5.1.1 Analysis of Inpatient Psychiatric Hospitalization Rate Between the Retrospective Period Month 1-3 and the Prospective Period Month 1 - 3 (Month 1-3 mITT)

CT-5.1.2 Analysis of Inpatient Psychiatric Hospitalization Rate Between the Retrospective Period Month 1-3 and the Prospective Period Month 1 - 3 (ITT Sample)

CT-5.1.3 Analysis of Inpatient Psychiatric Hospitalization Rate Between the Retrospective Period Month 1-3 and the Prospective Period Month 1 - 3 (Month 1-3 mITT and Completer)

CT-5.1.2.1 Number of Inpatient Psychiatric Hospital Stays Per Subject Between Retrospective Period and Prospective Period Month 1-3 (Month 1-3 mITT)

CT-5.1.2.2 Number of Inpatient Psychiatric Hospital Stays Per Subject Between Retrospective Period and Prospective Period Month 1-3 (ITT Sample)

CT-5.1.2.3 Cumulative Duration of Inpatient Psychiatric Hospitalization Per Subject Between Retrospective Period and Prospective Period Month 1-3 (Month 1-3 mITT)

CT-5.2.3.4 Cumulative Duration of Inpatient Psychiatric Hospitalization Per Subject Between Retrospective Period and Prospective Period Month 1-3 (ITT Sample)

CT-5.1.2.5 Mean Duration of Inpatient Psychiatric Hospitalization Per Subject Between Retrospective Period and Prospective Period Month 1-3 (Month 1-3 mITT)

CT-5.1.2.6 Mean Duration of Inpatient Psychiatric Hospitalization Per Subject Between Retrospective Period and Prospective Period Month 1-3 (ITT Sample)

CT-5.2.1 Summary of PDC for Month 1-3 Retrospective/Prospective Period (ITT Sample)

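### Counting stays already open when Months 1-3 begins can add retrospective but almost no prospective events to the primary endpoint, to the extent that earlier admissions are recorded

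*SAP*

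**What the plan says.** Under SAP 7.1.2, a stay belongs to Months 1-3 if it starts in the window, or if "The hospitalization starts before the start date of retrospective (or prospective) Months 1-3 and continues into Months 1-3". The retrospective window has "start date = (Date signing informed consent - 28*6 Days") and ends 85 days before consent. The prospective window has "start date = (Mycite start date) and end date = (Mycite start date + 28*3 - 1"). Each lasts 84 days.

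On the state of a subject when the prospective window opens, SAP 3.1 says "The first dose of Abilify MyCite is to be taken at the baseline (Day 1) visit (in the clinic) during onboarding", with an exception for a subject who has already taken that day's dose. Protocol 3.2.1 withdraws a subject who requires inpatient psychiatric hospitalisation during tolerability assessment or cross-titration. SAP 3.3 excludes subjects hospitalised for a psychiatric reason in the 4 weeks before consent "or at any time during the screening period". Protocol Table 3.4.3-1 has no such criterion, and the Amendment 1 log records that an exclusion on hospitalisation during screening was removed.

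On the retrospective side, eligibility asks for a hospitalisation at some time in the previous 48 months. The subject's "past psychiatric history for the 6 months prior to screening must be available" (SAP 3.1).

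On alternative analyses, SAP 7.1.3 says "the primary efficacy analysis will be performed on the mITT subjects who have completed the 3-month treatment only". Appendix 2 lists the same comparison in the ITT sample (table CT-5.1.2, "Analysis of Inpatient Psychiatric Hospitalization Rate Between the Retrospective Period Month 1-3 and the Prospective Period Month 1 - 3 (ITT Sample")) and in mITT completers (CT-5.1.3).

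**The concern.** A rule with identical wording for both periods looks neutral, but whether it is depends on where each window opens. The retrospective window opens on a date set only by counting back from consent, and no criterion requires the subject to be out of hospital then. The prospective window opens when the subject comes to clinic to start the product, so almost no open stay can cross into it.

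The trial has no concurrent control, so the two windows carry the whole comparison. An event source that acts on one side only produces a retrospective-minus-prospective difference without any treatment effect, and it favours MyCite. The visible alternative analyses change the set of subjects, not the counting rule. Listings EFF-1.1 and PDATA-13.1 cover the stays, but no visible table or test separates the carried-over ones. Parts of SAP 7.4 and Appendix 2 are redacted, so this can be said only of the visible text.

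**Working it through.** **Plan's own figure.** Discordant cells are 13.5% and 5% (Protocol 7.1, SAP 4), so pd = 0.185 and d = 0.085. The McNemar normal formula is n = (1.96·√pd + 0.8416·√(pd − d²))² / d². It gives 198.6, so 199 against the stated 200. Power at 224 with a single test at 0.05 is 84.6%.

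**Assumptions.** Mean stay L is not in the documents; I take 7, 10 and 14 days. The retrospective rate is held at the planned 15.5%, the admission rate is steady, there is no treatment effect and there is no prospective carry-over.

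**Spurious difference, common hazard.** A subject counts retrospectively if admitted in the 84-day window or in roughly the L days before it: 1 − exp(−λ(84 + L)) = 0.155. The prospective rate is 1 − exp(−84λ).

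| L (days) | Prospective rate | Difference | Single-look rejection favouring MyCite, n = 224 |
|---|---|---|---|
| 7 | 14.40% | 1.10 points | 5.0% |
| 10 | 13.97% | 1.53 points | 6.5% |
| 14 | 13.44% | 2.06 points | 8.8% |

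Rejection is the exact probability for the uncorrected McNemar test at two-sided 0.05, with the both-periods cell implied by the model (2.1-2.2%). Without carry-over it is 2.5%.

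**Clustered admissions.** With gamma frailty (shape 0.2, 0.5, 1):
- 7 days: 0.76, 0.95 and 1.02 points; rejection 4.9-5.0%.
- 14 days: 1.45, 1.78 and 1.91 points; rejection 8.3-8.8%.

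Clustering lowers the difference by up to about 30% but hardly changes rejection, because there are also fewer discordant pairs. The overall range is 0.76-2.06 points. That is 0.76/8.5 = 9% to 2.06/8.5 = 24% of the planned difference, or 1.7 to 4.6 of 224 subjects.

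**Three looks.** Simulated at 112, 157 and 224 subjects with the planned alphas 0.00312, 0.0139 and 0.04528, without futility or sample size increase: 4.6-5.0% at 7 days and 7.8-8.7% at 14 days.

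**Incomplete recording.** If half of the carried-over stays are recorded (assumed), L is replaced by L/2. At 7 days this gives 0.39-0.57 points and 3.6%; at 14 days, 0.76-1.10 points and 4.9-5.0%. If none are recorded, both are as under no carry-over.

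**Lower base rate.** With an assumed retrospective rate of 8%, common hazard and full recording: 0.59 points and 4.3% at 7 days, 1.10 points and 6.6% at 14 days.

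**Offsetting effect.** A subject in hospital on the first retrospective day cannot be newly admitted until discharge. At 14 days, λ = 0.00172 per day and the share in hospital is 14 × 0.00172 = 2.4%. The events lost are 0.024 × 14 × 0.00172 = 0.06 points, which is negligible.

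**The case against.** The strongest reply is that the bias may be zero. History is required only for the 6 months before screening, and listing PDATA-13.1 is titled for a 6-month retrospective period. Nothing states that a stay begun earlier is recorded with its dates. This stands as a condition on the size. It does not remove the point: the first limb of SAP 7.1.2 exists to count such stays, and the duration formula in SAP 7.4.1.2 truncates them at the window start, so the SAP expects some.

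The size also rests on an assumed length of stay and base rate. That stands, and the ranges above show it.

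A reader might infer from SAP 3.3 that prospective carry-over is impossible. The documents do not support that: the current protocol exclusions lack the screening bar and Amendment 1 removed one. The asymmetry rests instead on the Day 1 clinic visit and the withdrawal rule in Protocol 3.2.1. That rule does not cover subjects who enter without cross-titration, so the claim is almost no prospective carry-over, not none.

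A reader might also infer that the primary definition should be replaced. The overlap rule is explicit and prespecified, the protocol endpoint permits either reading, and the interim efficacy, futility and sample size rules use the same endpoint. The possible loss of power is material. The evidence supports an added analysis, not a substitution.

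**Conclusion.** The counting rule is symmetric in wording but not in effect. Any bias it creates favours MyCite, and this direction follows from the documents. The size does not: it depends on mean stay, on the retrospective rate and on how many stays begun before the look-back are recorded. With 7-14 days, 15.5% and full recording, it is 0.8-2.1 points and a single-look error toward MyCite of about 5-9% instead of 2.5%. Half recording gives 0.4-1.1 points and 3.6-5.0%, and no recording gives no bias. An 8% rate with full recording and a common hazard gives about 0.6-1.1 points and 4.3-6.6%.

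This does not show that a positive result would be an artefact: even the largest figure is about a quarter of the planned 8.5 points. It shows that the visible plan gives no way to see how much of the difference comes from the rule. The SAP should be amended. Confidence is medium because the recording of earlier stays is unknown.

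**What to change.** Keep the overlap rule as primary and add the following to SAP 7.1.3.

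- A named key sensitivity analysis: the Months 1-3 McNemar test, counting a stay only if its admission date lies between the start and end dates of Months 1-3 of that period, inclusive. Use the same admission-date definition in parallel analyses of Months 4-6 and Months 1-6, so that definitions are not mixed.
- For each period, the number of subjects who count only through a carried-over stay.
- A flag for admissions whose day or month was imputed into the window under SAP 5.1.4.2, with results with and without them. That rule dates an admission inside the window when only the day is missing and the year and month match the window start. A stay begun earlier in that calendar month would then pass as a new admission.
- A statement, made in advance, of how a disagreement with the primary result will be reported.

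Separately, reconcile SAP 3.3 with the protocol exclusion criteria on hospitalisation during screening.

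**Cost.** A few lines of SAP text and one table; SAP 7.4.1.2 already uses admission dates. The sensitivity analysis has less power if the planned 15.5% includes carried-over stays, which the documents do not state. Under the common-hazard rates, with the prospective cells kept at 5% and 2%, the difference is 14.4 − 7 = 7.4 points (7 days) or 13.4 − 7 = 6.4 points (14 days). Single-look power at 224 is then 76% or 66%, against about 85% as planned. Reaching 80% would need 248 or 309 completers, against a cap of 300. If the 15.5% counts admissions only, no power is lost.

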7.1.3 Sensitivity Analyses

As sensitivity analysis, the primary efficacy analysis will be performed on the mITT subjects who have completed the 3-month treatment only that is all subjects who are in study for at least 75 days (12 weeks adjusting for the 9 days allowed for visit window).

7.3 Subgroup Analyses

In earlier 2020, an outbreak of respiratory disease caused by a novel coronavirus named "Coronavirus Disease 2019" (COVID-19) had widely spread all over the world. On March 13, 2020, the President of the United States declared a national emergency in response to COVID-19. It is after this date, centers enrolled in this study had implemented remote visits

^a Martin BC, Wiley-Exley EK, Richards S, Domino ME, Carey TS, Sleath BL. Contrasting measures of adherence with simple drug use, medication switching, and therapeutic duplication. *Ann Pharmacother.* 2009 Jan;43(1):36-44.

^b Nau DP. [Accessed May 30, 2018]; Proportion of days covered (PDC) as a preferred method of measuring medication adherence. 2011 Available at: <http://www.pqaalliance.org/images/uploads/files/PQA%20PDC%20vs%20%20MPR.pdf>.

^c Karve S, Cleves MA, Helm M, Hudson TJ, West DS, Martin BC. Good and poor adherence: optimal cut-point for adherence measures using administrative claims data. *Curr Med Res Opin.* 2009 Sep;25(9):2303-10.

1.1 Secondary Endpoint

Protocol 31-201-301 Interim Analysis Plan

in response to this pandemic. In order to assess the effects of this change on the primary efficacy endpoint and secondary endpoint, subgroup analysis is planned.

The COVID subgroup is defined based on the time the subject started the study treatment: all subjects started Mycite treatment after March 13th will start the remote access or remote changes for all their visits and will be classified as COVID=Yes; subjects started the Mycite on or before March 13th will have COVID=No.

[figure not shown]

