7.1.1 Statistical Methods of Primary Efficacy Analysis

The primary analysis will be achieved by testing for statistically significant (at 2-sided overall alpha = 0.05). The analysis will be performed using a McNemar test on those who have hospitalization data during Months 1 to 3 prior to the screening period and during Months 1 to 3 after switch to Abilify MyCite.

Protocol 31-201-301 Interim Analysis Plan

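### The COVID=Yes before/after change in SAP 7.3 mixes MyCite with the move past 13 March 2020 for most or all of those subjects, and COVID=No is not a clean reference

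*SAP*

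**What the plan says.** SAP 7.3 notes the emergency declaration of 13 March 2020 and says that afterwards "centers enrolled in this study had implemented remote visits". It gives the purpose of the subgroup analysis as follows: "In order to assess the effects of this change on the primary efficacy endpoint and secondary endpoint, subgroup analysis is planned". The label depends on one date only. On one side, "all subjects started Mycite treatment after March 13th will start the remote access or remote changes for all their visits", and these subjects are COVID=Yes. On the other, "subjects started the Mycite on or before March 13th will have COVID=No".

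The windows are set in SAP 7.1.2. For retrospective Months 1-3: "start date = (Date signing informed consent - 28*6 Days) and end date = (Date of signing informed consent - 28*3-1 Days". Prospective Months 1-3 run from the MyCite start for 84 days.

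On the primary test, SAP 7.1.1 says: "The analysis will be performed using a McNemar test on those who have hospitalization data during Months 1 to 3 prior to the screening period", compared with Months 1 to 3 after the switch. It gives no adjustment for calendar time.

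**The concern.** In a mirror-image trial the control is the same subject at earlier dates. Anything that changes admission rates between the two windows enters the before/after difference, whichever subgroup the subject is in. The SAP uses the earlier half of the six-month look-back as its control, so the two windows begin 168 days plus the screening time apart. For a subject starting MyCite soon after the declaration, the control period lies in late 2019 and the treated period lies wholly in the pandemic.

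SAP 7.3 is the only efficacy analysis by pandemic era that can be read in the plan. A fall in admissions in the COVID=Yes row could be read as the MyCite effect holding up under remote care, when part or all of it could be a general change in admissions. The pooled primary test would take in the same shift.

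**Working it through.** **The plan's own figure.** SAP section 4 gives 200 completers for 80% power, with discordant pairs of 13.5% and 5%. With psi = 0.185 and d = 0.085, the McNemar normal approximation is n = [1.96·sqrt(psi) + 0.8416·sqrt(psi − d²)]² / d² = 198.6, so 199; power at n = 200 is 80.3%. The figure is reproduced. It is used below only to price the restricted analysis.

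**Inputs.** Cut-off 13 March 2020 (SAP 7.3). Retrospective window: consent − 168 to consent − 85 days. Prospective window: start to start + 83 days (both SAP 7.1.2). Consent-to-start gap s: up to 45 days (SAP section 3); a minimum of 1 day is assumed.

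**COVID=Yes, prospective window.** The start is on or after 14 March 2020, so the whole window is after the cut-off.

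**COVID=Yes, retrospective window, by consent date in 2020.**

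| Consent | Window | Days on or before 13 March |
|---|---|---|
| 6 June | 21 Dec 2019 to 13 Mar 2020 | 84 of 84 |
| 17 July | 31 Jan to 23 Apr | 43 of 84 |
| 18 July | 1 Feb to 24 Apr | 42 of 84 |
| 28 August | 13 Mar to 4 Jun | 1 of 84 |
| 29 August | 14 Mar to 5 Jun | 0 of 84 |

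Adding s: the window is wholly on or before the cut-off for any start up to 7 June (s = 1), and up to 21 July if s = 45. It is wholly after only for starts from 30 August (s = 1) or 13 October (s = 45).

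**COVID=No.** The prospective window ends by 13 March only if start + 83 ≤ 13 March 2020, that is, a start by 21 December 2019. Starts from 22 December 2019 to 13 March 2020 have prospective days after the cut-off: 83 of 84 for a 13 March start. Their retrospective windows all end before it.

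**How many COVID=Yes subjects straddle.** The documents give no last enrolment date. As an assumption range, if every subject had finished 168 prospective days by the SAP approval of 5 November 2020, the last start is 22 May 2020 and every COVID=Yes retrospective window is wholly before the cut-off. If only 84 days had been finished, the last start is 14 August 2020; that subject's retrospective window is 19% (s = 1) to 71% (s = 45) before it.

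**Size of the shift.** Assume no MyCite effect, the SAP's 15.5% retrospective rate, and an era-related fall r in admissions. The documents give no r. In fully straddling pairs the apparent drop is 15.5 × r:

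- r = 10%: 1.55 points
- r = 30%: 4.65 points
- r = 55%: 8.5 points, the whole design effect

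In the pooled test this is multiplied by the share f of fully straddling pairs. With f = 0.5 (assumed) and r = 30%, it is 0.5 × 4.65 = 2.3 points. Partly straddling pairs contribute less.

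**PDC.** The Months 1-6 look-back runs from consent − 168 to consent − 1. It is mostly before the cut-off only for consent by 5 June 2020, so the same mixing applies over a narrower range of dates.

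**The case against.** The strongest objection concerns purpose. SAP 7.3 sets out to assess the change to remote visits, not to isolate MyCite within COVID=Yes. On that view an era shift in the COVID=Yes row is what the analysis looks for, and the comparison that matters is Yes against No. This stands as a reading of the aim. But the readable text specifies no Yes-minus-No contrast of the paired changes, COVID=No is itself partly exposed, and such a contrast would still not separate remote visits from wider pandemic effects on admissions.

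It can also be said that COVID=No already supplies an unaffected estimate. It does so only for starts by 21 December 2019, and the label does not pick those subjects out.

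Four stronger readings might be inferred and are not supported:

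- **That period and era coincide throughout COVID=Yes.** The label has no end date. Later consents give mixed windows, and from 29 August 2020 both windows fall after the cut-off.
- **That the 5 November 2020 approval rules out analysed pairs lying wholly after 13 March.** It dates the document; it is not a data cut-off.
- **That remote visits reduced the recording of admissions.** Protocol 3.7.1.4 and 3.7.2.1.1 take them from health records and continuous reporting. Nothing shows poorer capture.
- **That the subgroup tables are missing.** A figure is not shown and parts of Appendix 2 are redacted, so this cannot be said.

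Finally, lack of adjustment for time is a limit of any mirror-image trial. That is true, but here the SAP itself names a dated change and plans an analysis of it.

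**Conclusion.** The point holds in conditional form. Every COVID=Yes prospective window is after 13 March 2020. The retrospective window is wholly on or before that date for consent by 6 June and more than half before for consent by 17 July. For those subjects the within-subgroup change combines three things that it cannot separate. Whether they are most or all of COVID=Yes depends on the last enrolment date. The pooled primary result is affected in proportion to the straddling pairs, whose number the documents do not give.

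The direction and size of any era effect are not in the documents; the point figures are illustrations under a null MyCite effect. The date results rest only on the SAP's formulas and a screening gap of 1 to 45 days. This should be corrected because it bears on how both the subgroup row and the primary result are read. It does not show that the primary result is wrong.

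**What to change.** In SAP 7.3:

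1. Add, as a sensitivity analysis, the primary McNemar test restricted to pairs whose prospective Months 1-3 window ended on or before 13 March 2020 (MyCite start by 21 December 2019), with the number of pairs.
2. Report any pairs with both windows wholly after 13 March separately. They compare two parts of the pandemic and should not be pooled with the first set as free of era effects.
3. State that the COVID=Yes before/after difference is not by itself an estimate of the MyCite effect.

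The cost is a paragraph and a table; the window dates are already derived under SAP 7.1.2. The restricted test has fewer pairs and less power. With the plan's discordance rates and two-sided 0.05, power = Φ[(0.085·sqrt(n) − 1.96·sqrt(0.185)) / sqrt(0.185 − 0.085²)]. For assumed counts of 150, 100 and 50 pairs this is about 68%, 51% and 28%. The result should therefore be read by its estimate and interval, not by significance. It removes the 13 March shift but not the other limits of a mirror-image comparison.
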